#### 14.3.3 Simulation and Sample Size Calculations

The TITE-CRM manual details methods for utilizing trial simulation in order to obtain estimated posterior probabilities on toxicity estimates. We utilize the

simulation program to determine the efficacy of our trial and obtain estimates for needed sample size. While there is no exact power calculation for this type of trial, the effectiveness of the trial's sample size can be determined by looking at the stability of the posterior probability under different prior probabilities. We ran 1000 simulations under various increasing and decreasing prior probability estimates utilizing the previously described rules and assumptions for this trial and found that we will be able to determine the MTD with 18 patients. Simulations showed that approximately 98% of the time the trial will come to completion after 18 patients and the MTD will fall between the 2nd and 3rd dose level more than 95% of the time. Therefore, the sample size of this adaptive phase I/II study will be 18 patients.

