As for the rationale for the proposed expansion cohort, this is based on the promising finding of the dose-escalation phase of the study. After enrollment of the 18 patients for the dose-escalation phase, 8 patients were treated with DSF of 250 mg/day (dose level 2) and 10 patients with 375 mg/day (dose level 3). Three dose-limiting toxicities (DLTs) were observed: 1 with 250 mg/day (grade 2 urinary incontinence and ataxia), and 2 with 375 mg/day (both grade 3 elevated liver enzymes). The TITE-CRM model estimated the DLT probability of DSF to be 10% (95% CI: 3-29%) at 250 mg/day, and 21% (95% CI: 7-42%) at 375 mg/day. Thus, we have declared that the MTD of DSF in combination with RT/TMZ/Cu for GBM is 375 mg/day, and the recommended phase II dose is 250 mg/day. Furthermore, tumor mutations were evaluated with next-generation sequencing for all patients to explore possible biomarkers for response. Notably, GBM patients with *IDH* (n = 6), *BRAF* (n = 2), and *NF1* (n = 1) mutations exhibited much better PFS and OS than those without these mutations (n = 9): 1-year PFS of 100% vs 22%, respectively, p = 0.001; 1-year OS of 100% vs 42%, respectively, p = 0.006. Given that the historical PFS and OS of newly diagnosed GBM patients treated with RT and TMZ is approximately 27% and 60% at one year [4], respectively, the preliminary data of this molecular subset of GBM are thought-provoking and raise the possibility that these mutations make GBM tumors more sensitive to DSF/Cu in combination with chemoradiotherapy. Interestingly, all three mutations, which affect approximately 15-20% of GBM tumors, make tumor cells more dependent on glutamate for cellular metabolism [68-70]. As DSF metabolite can affect glutamate uptake, this may be the biological mechanism for the improved outcomes for GBM with these mutations. Thus, we have proposed to add an expansion cohort to this phase I/II study to treat additional GBM patients with *IDH*, *BRAF*, or *NF1* mutations to increase the statistical power of our preliminary finding.

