## 14.0 STATISTICAL CONSIDERATIONS

### 14.1 Definition of Primary Endpoint

The maximum tolerated dose (MTD) of DSF with concurrent RT+TMZ will be defined as the dose associated with a 20% probability of dose-limiting toxicity (DLT). Toxicity will be coded using CTCAE version 4.0, and DLT will be defined as toxicity that occurs within 18 weeks from the first day of RT and is possibly, probably or definitely related to DSF/Cu (or 12 weeks from the completion of RT if there is a delay/interruption of RT).

For the expansion cohort of GBM with *IDH*, *BRAF*, and *NF1* mutations, the overall survival (OS) of this molecularly-defined cohort will be measured from the first day of RT.

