The Time-to-Event Continual Reassessment Method (TITE-CRM) proposed by Cheung and Chappell is an adaptive Phase I design [80]. In a TITE-CRM clinical trial, patients enroll as they become available to be studied. Each participant is assigned to a dose level from a set of dose levels pre-defined by investigators and is monitored for DLTs over time. The design is adaptive in that the dose level assigned to a newly enrolled patient depends on the dose level assignments and DLT outcomes of the patients already in the study. A patient's observation period ends at the occurrence of a DLT, or if a DLT does not occur, after a fixed time T of follow-up. The trial ends when a fixed number of patients,  $n$ , have been observed. Once the final patient has been observed, the MTD can be estimated using the available data. The TITE-CRM differs from the traditional CRM in that the estimation process is weighted to account for the proportion of the observation period that each currently enrolled patient has been observed. By not requiring complete observation before the enrollment of the next patient, new participants can be assigned a dose and begin evaluation as they become available, subsequently shortening the overall duration of the study.

The Biostatistics Unit at the University of Michigan Comprehensive Cancer Center has developed a program `titecrm.sas` for SAS 9 (SAS Institute, Inc.; Cary, NC) that makes all of the calculations necessary to determine dose allocation of a trial in real-time. They have also developed simulation programs that allow the user to determine the efficacy of the trial based on *a priori* estimates of the probabilities of toxicity and necessary sample sizes.

In order to properly utilize this type of trial, a few assumptions and many rules must be determined before the start of the trial. The main assumption that must be determined is how many different dose levels will be included in the trial and *a priori* estimates of the probability of a DLT at each of those dose levels. For this trial, we have 4 dose levels ( $d_1, \dots, d_4$ ) ranging from 125mg PO daily to 500 mg PO daily, with initial toxicity probability estimates ( $p_1, \dots, p_4$ ) ranging from 0.05 to 0.30, respectively. The following table shows the dose design with associated estimated probabilities of toxicity.

Dose Escalation Schedule		
Dose Level	Dose of DSF	Initial Toxicity Estimate
Level 1	125 mg PO daily	0.05
Level 2	250 mg PO daily	0.10

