#### 14.3.2 TITE-CRM Design for the Dose-escalation Phase

The starting dose can have a large impact on the properties of the design. After the trial is completed, most information about the MTD will be obtained if many patients are treated at or near the MTD, thus the sooner the choice of dose can converge on the MTD the more effective the trial will be. However, with concerns about safety we will start at the one dose level lower than the expected MTD. Therefore, our starting dose for this trial will be 250 mg PO daily.

The next thing to be considered is the dose escalation rules. For this trial, we will only allow a single dose level escalation per new patient enrolled on the trial. Therefore, if the previous patient was treated at dose level,  $d_k$ , then a new patient can only be treated at dose levels  $d_{k+1}$  or lower. In order to determine at which level to treat the new patient, we will use a non-weighted, cumulative time of exposure approach. The total length of follow-up for DLT for any patient is 18 weeks. In order to efficiently and effectively determine the MTD, we allow for a dose change when the cumulative time of exposure is 18 weeks. Also, since previously published data shows that toxic events occur evenly throughout the time of the study we will not implement a weighting function. The dose for the next patient is selected so that the estimated probability at that dose is close to the target level. A feature of the dose escalation part of the TITE-CRM program is the flexibility in specifying the margin for the dose selection. This allows the selection of the dose level for the next patient that may have an estimated probability of toxicity larger than the target level but less than the target level plus the margin. It finds the dose closest to the target probability even if it has a higher estimated probability. For this trial we set the admissible margin to be 5%, therefore, the MTD will be chosen as the dose that yields a posterior toxicity estimate closest to 20% while being between 15% and 25%. The admissible margin is also used to help determine stopping rules for the trial. In order to account for the possibility of poor initial outcomes we will employ a run-in of 6 patients, meaning that the minimum number of treated patients will be 6. If after these 6 patients, or any other time during the trial, the lowest dose level has a posterior probability higher than 25% then the trial will stop.

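### The more-than-95% chance of the MTD landing at dose level 2 or 3, cited in support of n=18, cannot be reproduced from the stated TITE-CRM design; about 70% is obtained under the plan's own toxicity curve

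*Combined protocol and SAP*

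**What the plan says.** Section 14.1 takes the MTD as a primary endpoint, "defined as the dose associated with a 20% probability of dose-limiting toxicity (DLT"). Sections 14.3.1 and 14.3.2 fix most of the design:

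- four dose levels with initial toxicity estimates "ranging from 0.05 to 0.30, respectively" (0.05, 0.10, 0.20, 0.30 in the table);
- "our starting dose for this trial will be 250 mg PO daily", which is level 2;
- "we will only allow a single dose level escalation per new patient enrolled on the trial";
- an 18-week DLT window, 18 weeks of cumulative exposure before a dose change, and toxicity assumed to be spread evenly over the window;
- a 5-point margin around the 20% target, and stopping after 6 or more patients if the estimate for level 1 exceeds 25%.

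Section 14.3.3 reports 1000 simulations under various increasing and decreasing prior estimates. It gives two results: "approximately 98% of the time the trial will come to completion after 18 patients", and an MTD between the 2nd and 3rd "dose level more than 95% of the time". From these it concludes that "the sample size of this adaptive phase I/II study will be 18 patients".

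Section 1.3 reports the outcome: 1 DLT in 8 patients at level 2 and 2 in 10 at level 3, with estimated DLT probabilities of 10% (95% interval 3-29%) and 21% (7-42%). It then states: "Thus, we have declared that the MTD of DSF in combination with RT/TMZ/Cu for GBM is 375 mg/day", with 250 mg/day as the recommended phase II dose.

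**The concern.** Eighteen patients on four closely spaced levels give little information to separate a 20% DLT rate from a 30% one. A probability above 95% of ending at one of the two middle levels is surprising when the level above has an assumed DLT rate only 10 points over target. The text also says that the prior estimates were varied and that stability of the posterior was examined. It does not name a fixed true curve, and a selection probability has no meaning without one.

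At stake is the statement of how reliable the design was for a primary endpoint, and the step from that statement to n=18. If the figure is repeated when the MTD is reported, readers will credit the design with more reliability than its stated rules can be shown to have.

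**Working it through.** **Inputs from the plan.** n = 18; target 20%; skeleton s = 0.05, 0.10, 0.20, 0.30; start at level 2; one-level steps; 18-week window; 18 weeks of cumulative exposure before a dose change; uniform DLT times; stop after 6 patients if level 1 exceeds 25%.

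**Inputs assumed because the plan does not state them.** A power model, p_i = s_i^exp(θ) with θ ~ Normal(0, SD²), or a one-parameter logistic model with intercept 3; the prior SD; the accrual interval (1 to 20 weeks per patient); the true curve. A patient without DLT after t weeks contributes 1 − w·p_i with w = min(t/18, 1); a patient with DLT contributes p_i. The selected level is the one with the posterior estimate closest to 20%.

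**Step 1: calibrate the prior on the trial's own report.** Assuming full follow-up, the posterior is proportional to prior(θ) × p_2(1 − p_2)^7 × p_3²(1 − p_3)^8.

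| Source | 95% interval, level 2 | 95% interval, level 3 |
|---|---|---|
| Section 1.3 | 3-29% | 7-42% |
| Power SD 0.5-0.75, logistic SD 0.25-0.4 | 2-3% to 27-29% | 7-8% to 40-43% |
| Power SD 0.20 | 4-20% | 11-32% |

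The moderate priors match the reported intervals and the tight one does not. The point estimates separate the priors poorly; the interval widths do the work.

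**Step 2: reproduce the companion figure.** With the plan's curve as truth, completion is 100% minus early stopping. At power SD 0.65 this is 100 − 2.2 = 97.8%, in line with the stated 98%.

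**Step 3: test the figure above 95%.** Truth is the plan's curve; entries are % of simulated trials, 2000 to 4000 per setting.

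| Prior | Level 1 | Level 2 | Level 3 | Level 4 | Early stop | Level 2 or 3 |
|---|---|---|---|---|---|---|
| Power SD 0.5 | 1.3 | 24.0 | 49.9 | 24.6 | 0.2 | 24.0 + 49.9 = 73.9 |
| Power SD 0.65 | 1.6 | 23.6 | 45.7 | 26.9 | 2.2 | 23.6 + 45.7 = 69.3 |
| Power SD 0.75 | 2.1 | 22.5 | 43.8 | 27.6 | 4.0 | 22.5 + 43.8 = 66.3 |
| Logistic SD 0.3 | 1.7 | 24.2 | 45.3 | 27.4 | 1.4 | 24.2 + 45.3 = 69.5 |

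Over all compatible settings and separate runs the last column spans about 62-76%. Simulation error is small: √(0.70 × 0.30 / 2000) = 1.0 point. Changing accrual from one patient per week to one per 20 weeks moves the SD 0.65 result only between 69% and 73%. Counting completed trials alone gives 66-75%. Counting only trials whose chosen dose has an estimate inside 15-25% gives 67-76%. Wider priors give 44-64%.

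**Step 4: find where 95% is exceeded.**

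- Tight prior, plan's curve as truth: power SD 0.20 gives 97-98%, with no early stops; SD 0.25 gives 86-89%. At SD 0.15 the figure is about 100%, but the design hardly responds to data: with all true rates doubled (level 3 at 40%) it still selects level 3 in 79% of trials.
- Steep true curve (0.02/0.08/0.30/0.60): 96% at SD 0.5, and 91-92% at SD 0.65-0.75.
- Other true curves at SD 0.5-0.75: skeleton × 1.5, 76-88%; 0.05/0.10/0.20/0.50, 82-87%; flat 20%, 43-59%; skeleton halved, 26-30%.

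**Step 5: gauge the sample size.** Under the plan's curve at SD 0.65, even 100 patients give about 88%.

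**The case against.** The strongest reply is that Section 14.3.3 never says the figure applies when truth equals the skeleton. It refers to a set of scenarios that it does not list, run in a SAS program whose settings are not given. Under the plan's own curve the result runs from 44% to about 100% depending on the prior, so no single number follows from the written rules. This stands, and it limits the finding. A reader might infer that the design cannot deliver the stated figure; the documents do not support that, because a very tight prior or a very steep true curve can each produce it. Nor does 98% completion alone identify the prior, since completion is about 94-99.9% across the compatible range. What remains is that the tight prior conflicts with the intervals in Section 1.3 and with about 2% early stopping, and that no steep curve is documented.

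The phrase about falling between the two levels could also mean that the 20% dose lies between 250 and 375 mg. That would not help: if the level 2 estimate is at or below 20% and the level 3 estimate at or above it, the closest level is 2 or 3. The event is therefore contained in the one tested.

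A reader might further infer that the declared MTD and RP2D rest on the overstated figure. They do not. Section 1.3 derives them from the observed DLTs and the fitted posterior and prints the wide intervals. Once data are in hand, those intervals describe the uncertainty and a pre-trial selection frequency does not. Escalation is also complete, with all 18 patients at levels 2 and 3. Finally, the figure is not the sole support for n=18, because posterior stability and completion are cited too.

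**Conclusion.** The more-than-95% figure is not reproducible from the stated design. Under the plan's own curve, with a prior that fits the trial's reported intervals and stated completion rate, it is centrally about 70%, which is 95 − 70 = 25 points lower. Even the top of the range falls 95 − 76 = 19 points short. Level 4 is selected in about 23-28% of trials. Level 3, the true MTD under that curve, is selected in only about 43-53%, so counting levels 2 and 3 together already flatters the design.

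What is overstated is the prospective reliability of the escalation design and, with it, part of the justification for 18 patients. Nothing here shows the declared doses to be wrong. The size rests on an assumed power or one-parameter logistic model, full follow-up in the calibration, uniform DLT times and the plan's skeleton as truth. The internal model of the SAS program cannot be seen from the documents. The point should be corrected, but it calls for no change to the conduct of the trial.

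**What to change.** Re-run the existing simulation program and replace the sentence in Section 14.3.3 with a small table. It should give the selection probability for each dose level and the early-stop probability, under the plan's curve and two or three named alternative true curves. State the model form, prior variance and accrual rate beside it. The 70% computed here should not simply be written in, because it depends on assumed settings.

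If the settings cannot be recovered, withdraw the statement and do not cite it as the design's reliability when the MTD is reported; the credible intervals in Section 1.3 serve that purpose.

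The cost is a short re-run, a wording change and probably a less favourable stated figure. No patients, data or treatment rules are affected.

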#### **14.3.4 Workflow**

The first patient will be enrolled on the trial and treated at the 250 mg PO daily dose level, which is one dose level below the hypothesized MTD. That patient will be entered into the titecrm.sas program and follow-up will begin from start of treatment (RT+TMZ+DSF+Cu). Although the entire study duration is 34 weeks or at the completion of adjuvant DSF, for the purposes of DLT evaluation, the patient will be followed from start of treatment until the patient completes 18 weeks of follow-up, has a DLT, or is lost to follow-up. If any of these endpoints occur, the statistician will be notified and the date corresponding to the event will be entered into the program. While there is a maximum follow-up of 18 weeks for observation of possible DLTs, sometimes patients have a delay in their treatment resulting in the need for a prolonged observation period (at least 12 weeks after completion of RT if there is delay/interruption of RT). This delay will be accounted for as needed for this study to ensure completed 18 week follow-up. When a new patient is enrolled on the trial the statistician will be notified of the date of enrollment. At this time the statistician will update the follow-up for all patients currently on the trial and determine the dose that will be administered for the new patient. We will utilize the cumulative time of exposure method which will allow the contribution of patients with no DLT at this time to be partially weighted consistent with their time observed. At this point, the program provides a summary of the number of patients treated at each dose so far, along with the number of DLTs that have occurred. The posterior probability and 95% credible intervals of dose limiting toxicity for each dose level is calculated. At this point, the model determines the dose level that has an estimated toxicity rate closest to 20% within the 5% admissible margin. The newly enrolled patient will be enrolled in the corresponding dose level if that dose level is within one dose jump from the dose level the most current patient is enrolled on. If the suggested dose level is more than one dose level from the current dose level, the next patient will be enrolled on the dose level that is closest to the current level in the direction of the dose level determined from the estimated posterior probability. This continues until the trial has accrued all 18 patients or, if after 6 patients are enrolled, the estimated posterior probability for the lowest dose level is higher than 25%.

#### **14.3.5 Sample Size for the Dose-expansion Phase**

To further explore the effect of the addition of DSF/Cu to standard chemoradiotherapy for the subset of GBM with *IDH/BRAF/NF1* mutations, we propose to add an expansion cohort to further confirm that the addition of DSF/Cu to chemoradiotherapy may be a promising strategy to treat GBM with these mutations. Given historical data for a cohort of GBM is not readily available, some assumptions are used to derive a historical control benchmark. GBM with *BRAF* or *NF1* mutations are not known to have different prognosis than typical *IDH*-wildtype GBM [81,82], with historical OS of approximately 30% at 2 years and 10% at 5 years [3,83,84]. Both *BRAF* and *NF1* mutations affect the RAS/MAPK pathway and can also occur in the same patient, thus we will combine both mutations into one molecular cohort. However, *IDH*-mutant GBM is known to have better OS than *IDH*-wildtype GBM, with 2 year OS of approximately 50% and 5 year OS of approximately 20% [85], so we will define the second molecular cohort by the presence of *IDH* mutation. Therefore, a cohort with equal proportion of *IDH*-mutant GBM and *BRAF/NF1*-mutant GBM should theoretically have 2 year OS of 40% and 5-year OS of 15%. Based on such assumptions, a sample size of 24 patients (including 12 with *IDH* mutations and 12 with *BRAF/NF1* mutations) would provide 80% power with one-sided alpha of 0.10 to detect an improvement of 2-year OS from historical 40% to 60% (or a hazard ratio of 0.55). Since we have already enrolled 9 patients with these mutations (6 with *IDH* mutation, 2 with *BRAF* mutation, and 1 with *NF1* mutation), only additional 15 patients will be needed: 6 with *IDH* mutation, 9 patients with *BRAF* and/or *NF1* mutations. For the dose-expansion phase, patients are considered evaluable if a patient has received at least 4 weeks of DSF with RT, at either the MTD (375mg/day) or the RP2D (250mg/day). Inevaluable patients will be replaced.

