#### **14.4 Analytic Plan for Secondary and Exploratory Endpoints**

Adverse events will be tabulated by type and grade.

Descriptive statistics will be used to summarize and compare concentration of ditiocarb-copper complex and glutamate metabolites in plasma and tumor tissue, including median and range.

The cox proportional hazard models will be used to assess for associations between intratumor drug concentration with tumor control and survival.

The Kaplan-Meier product-limit method will be used to estimate tumor control and survival probabilities.

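### The stated alpha of 0.10 for expansion-phase OS does not hold for the planned 24 patients, because 9 of them were counted after their 1-year survival was known

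*Combined protocol and SAP*

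**What the plan says.** Section 14.1 makes OS from the first day of RT the expansion-phase primary endpoint. Section 14.3.5 sets N = 24 (12 IDH, 12 BRAF/NF1) for 80% power with "one-sided alpha of 0.10 to detect an improvement of 2-year OS from historical 40% to 60% (or a hazard ratio of 0.55"). The 40% is the average of two benchmarks. BRAF/NF1 tumours are treated like typical IDH-wildtype disease, "with historical OS of approximately 30% at 2 years and 10% at 5 years", and IDH-mutant tumours are given 50% and 20% at the same times.

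The section continues: "Since we have already enrolled 9 patients with these mutations" (6 IDH, 3 BRAF/NF1). Only 15 more are therefore sought, 6 IDH and 9 BRAF/NF1. It adds "Inevaluable patients will be replaced" without saying from which cohort.

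Section 1.3 compares those nine with the nine patients without the mutations: "1-year OS of 100% vs 42%, respectively, p = 0.006". It presents this as the rationale for the expansion.

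No section names a test of OS against the benchmark. Section 14.4 says "The Kaplan-Meier product-limit method will be used to estimate tumor control and survival probabilities" and keeps Cox models for drug concentration. Survival is collected by chart review 2 years after the patient comes off study (5.13), or on a form due 2 years after the last disulfiram dose (11.0).

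**The concern.** An alpha of 0.10 assumes that a patient's survival is unknown when that patient is committed to the analysis. For nine of the 24 it was not. Their first year had been observed, was free of deaths, and prompted the decision to test the hypothesis. A one-sample test that counts their time from first RT credits them with expected deaths in a year when none could occur. This pushes the result toward success whether or not the treatment works.

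The second issue is the pooled null. If the final mix is richer in IDH tumours than 12:12, the correct average benchmark is above 40% and the test becomes too easy. If it is poorer, power is lost.

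At stake is whether a positive result could be read as evidence at the stated error rate.

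**Working it through.** **Inputs.** From 14.3.5: N = 24, one-sided alpha 0.10 (critical value 1.2816), 2-year OS 40% against 60%, benchmarks at 2/5 years of 50%/20% (IDH) and 30%/10% (BRAF/NF1), and 9 earlier patients at 6:3 plus 15 new at 6:9. Assumed: no dropout, everyone cut at 2 years from first RT, and reference curves that are piecewise exponential through the benchmarks.

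**The plan's own figure.** ln 0.6 / ln 0.4 = 0.557, stated as 0.55. Events needed: (1.2816 + 0.8416)² / (ln 0.55)² = 12.6, so 13 events, which give 80.9% power. A one-sample log-rank at 2 years with HR 0.55 and an exponential 40% null has asymptotic power 78.6%. The stated 80% is about right for that test. An exact binomial on 2-year survivors gives 79% power at alpha 0.114 (13 or more of 24) or 65% at alpha 0.053 (14 or more).

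**Test used below.** O is observed deaths and E is the summed null cumulative hazard to death or 2 years. Z = (E − O)/√E (null variance) or (E − O)/√((E + O)/2) (average variance). Ranges run from the first form to the second; figures are from simulation (200,000 runs per setting in the main runs). Per-cohort nulls are used first, to keep the mix question separate.

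**Nine patients alive at 1 year, no treatment effect.** A hand calculation shows the mechanism.
- Yearly null hazards to 2 years: −ln 0.5 / 2 = 0.3466 (IDH) and −ln 0.3 / 2 = 0.602 (BRAF/NF1).
- First-year credit from the nine: 6 × 0.3466 + 3 × 0.602 = 3.89 expected deaths, with none possible.
- Their second-year deaths: 6 × (1 − √0.5) + 3 × (1 − √0.3) = 1.76 + 1.36 = 3.11.
- Deaths in the 15 new patients: 6 × 0.5 + 9 × 0.7 = 9.3.
- Mean O = 3.11 + 9.3 = 12.41; mean E = 12.41 + 3.89 = 16.30.
- Success needs E − O > 1.2816 × √16.30 = 5.17. Its mean is 3.89 and its SD about √12.41 = 3.52. (5.17 − 3.89)/3.52 = 0.36, a probability of about 0.36.

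Simulation gives 0.35 to 0.39 at 2 years and 0.32 to 0.36 at 2.65 years. The exponential shape implies 1-year OS of √0.5 = 71% (IDH) and √0.3 = 55% (BRAF/NF1). If the true figures are 75–80% and 60–65%, the rate is 0.24 to 0.33 when the test uses those points, and up to 0.37 when it keeps the exponential curve.

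**Delayed entry of the nine at 1 year, 2-year cut.** Alpha is 0.087 to 0.107 and power 0.70 to 0.74. The 15 new patients alone have power 0.60 to 0.65.

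**The pooled null.** The correct average is 0.30 + 0.20 × IDH share, which equals 40% only at one half. Alpha of a nominal 0.10 log-rank at 2 years, all patients prospective:

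| IDH : BRAF/NF1 | Weighted null | Alpha, pooled 40% |
|---|---|---|
| 12:12 | 40.0% | 0.080–0.099 |
| 14:10 | 41.7% | 0.11–0.13 |
| 12:6 | 43.3% | 0.13–0.16 |

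Per-cohort nulls keep alpha at 0.086 to 0.107 at every mix tried.

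**Shape of the reference curve.** With all 24 followed from first RT, an exponential per-cohort null gives alpha 0.087 to 0.106 if it is true. If true 1-year OS is 75–80%/60–65%, it gives 0.105 to 0.151. With delayed entry of the nine, the same misfit gives 0.07 to 0.10.

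**The case against.** - **The mix is controlled.** The 6 and 9 still to be enrolled are chosen to turn 6:3 into 12:12, and with quotas by cohort, replacement within cohort is the natural reading. This stands. A reader might infer that the pooled null inflates alpha in the trial as planned. It does not: at 12:12 it holds alpha.
- **The unnamed test is missing detail.** The plan gives alpha, null, alternative and time origin. A reader might infer that the 80% or the 24 is wrong, but a standard one-sample log-rank roughly reproduces them. Nor should the binomial's 65% be set against a log-rank's power as a loss, because the two run at different alphas.
- **Per-cohort benchmarks are not a full remedy.** They repair only the null. They supply neither a test nor a cut-off, and leave the nine patients' problem untouched. This stands.
- **Pooling escalation patients can be legitimate.** It would be if their inclusion had been fixed before outcomes were seen. Here the rationale cites the outcomes. A reader might go further and infer that patients were picked for having survived. The documents do not say that; membership is defined by mutation, and the calculation needs no such intent.
- **The 100% may be a Kaplan-Meier estimate** with some of the nine followed for less than a year. The plan gives no individual follow-up, so the size of the inflation is conditional on all nine being known alive at 1 year.

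**Conclusion.** The main point holds. The one-sided alpha of 0.10 does not apply to the 9 + 15 patients that 14.3.5 plans to analyse. If the nine are known alive at 1 year, the false-positive rate of a 2-year log-rank is about 0.35 to 0.39, or 0.24 to 0.37 under more favourable 1-year benchmarks. Even the lowest figure is more than twice the stated level. These rates rest on the assumed curve shape and on a log-rank being the intended test.

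The mix dependence of the 40% null is secondary and conditional on a missed quota. The analysis time also needs stating. The off-study and last-dose dates cannot serve, because progression is a reason for stopping disulfiram (5.12), which makes them depend on outcome.

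**What to change.** Amend 14.3.5 to state the following.

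1. OS is tested by a one-sample log-rank at one-sided 0.10, with the variance form named. Each patient's expected hazard comes from their own cohort's benchmark (50%/20% or 30%/10% at 2/5 years). Inevaluable patients are replaced within the same cohort.
2. At-risk time for the nine earlier patients starts at their follow-up when the expansion was proposed. Power is restated for the actual 9 + 15 design: about 0.70 to 0.74, with alpha 0.087 to 0.107, if that follow-up is 1 year and the cut is 2 years. The 15 new patients are also reported alone (power 0.60 to 0.65). This matters because section 1.3 reports the nine as progression-free at 1 year too, and delayed entry does not remove that knowledge.
3. The assumed shape of the reference curve before 2 years is given, with a sensitivity analysis over plausible 1-year values.
4. The analysis time is fixed from the first day of RT. Two years is the minimum, and a longer fixed time is acceptable.

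The cost is one paragraph and a stated power below 80%. With a 2-year cut no extra patients, visits or data are needed, since every planned chart review falls more than 2 years after first RT.
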